7.4 Vital Signs and Physical Exam

Descriptive statistics for vital signs parameter will be provided for scheduled visit and for the changes from Baseline at Week 12 and Week 26. “Final” visit (Week 26 (Final)) will be defined as the last post-baseline available observation during the treatment period. Nominal eCRF visit will be used as analysis visit.

Physical exam will be provided in a subject-by-subject listing.

7.5 Analysis Visit Definition

All efficacy variables, vital signs, and laboratory data will be summarized by analysis visit.

Analysis visit will be assigned according to the following algorithm to summarize the efficacy data by proper visit window interval. Study day is calculated as visit date minus the date of first application plus 1. Visit during treatment period will be used for analysis visits of Baseline to Week 26 assignment. Week 30 Follow-up will be the post-treatment/follow-up visit.

If multiple measurements are taken in the same interval, the one closest to the target study day will be used for the analysis. If two measurements are taken with equal differences in timing compared with the target date, the nominal visit number (recorded on the CRF page) will be used.

Table 2 Analysis Visit for Efficacy Data Summaries

Analysis Visit	Analysis Visit Number in Derived Dataset	Target Study Day	Visit Window for IGA, Pruritus, % BSA(Study Day)
Screening	-1	-	[< 1]
Baseline	1	1	[<= 1]
Week 4	2	29	[2 – 42]
Week 8	3	57	[43 – 70]
Week 12	4	85	[71 – 112]
Week 20	5	141	[113 – 161]
Week 26	6	183	[162- 196]
Week 26(LOCF)	6.999	-	Last available data during treatment period, including Baseline.
Week 30 Follow-up	7	-	Last available data during Follow-up data.

For efficacy data, screening visit will be assigned to analysis visit of screening as recorded on CRF page. If multiple measurements of screening due to rescreening or other unexpected reasons, the screening visit closest to date of first application will be chosen. If there is missing measurement at Baseline, Screening data will be used to impute the missing baseline data, if necessary, i.e. Baseline will be the last available data prior to first application. Only scheduled visit will be assigned into appropriate analysis visit; unscheduled visit will not be assigned to analysis visit, therefore, not in the summary.

When assigning the analysis visits for vital signs, no visit window will be applied; Nominal eCRF visit will be used as analysis visit for summaries.

When assigning the analysis visits for laboratory data, no visit window will be applied, however, the following rules will be applied:

1. If sample date/time is prior to date/time of first application, the data will be considered as screening visit. If multiple measurements of screening due to rescreening, retest or other unexpected reasons, the data closest to date of first application will be chosen.
2. Lab data from scheduled visit will be considered first when assigning analysis visit of each scheduled visit. If there is no data from scheduled visit available within the visit window, the last of those corresponding unscheduled visit will be considered for assignment of analysis visits.

3. When assigning Final visit, the lab data from the last post-baseline scheduled visit during treatment period will be considered first. If the last scheduled visit during treatment period have missing lab data due to any reason and there are subsequent unscheduled lab data available, the last of those corresponding unscheduled lab data will be assigned as Final visit. Otherwise, the previous visit lab data will be considered in the same manner.

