7.3.3 Laboratory Parameters

Analysis visit will be applied for the laboratory parameter summaries.

Descriptive statistics for each laboratory parameter will be provided for scheduled visit and for the changes from Screening at each post-baseline visit. “Final” visit (Week 26 (Final)) will be defined as the last post-baseline available observation during the treatment period.

A shift table for the laboratory data at Screening versus Final will be constructed for laboratory parameters for which numeric reference ranges are available. The number of subjects below, within, and above the laboratory reference ranges at Screening versus Final will be summarized.

For each laboratory test, a complete data listing will be provided for subjects who have any laboratory results outside the reference ranges, and for subjects who have any laboratory results with clinical significance.

Plot of mean change from screening and spaghetti plot (all-subjects-in-one figure or selective individual subject figure) will be used to explore the trend of laboratory data change over the study, especially for serum albumin-adjusted calcium, urine calcium/creatinine ratio, phosphorus, PTH. Box-and-Whisker plots for PTH and Calcium/Creatinine ratio by visit will be constructed for data exploration.

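### Early-termination vital signs, and probably laboratory values, can be reported as Week 26, because SAP 7.5 gives the Day 162–196 window only to the efficacy variables

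*SAP*

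**What the plan says.** **Schedule.** Protocol Table 2 and SAP Table 1 each give Week 26 and ET a single column (V5 in the protocol, V7 in the SAP). A footnote in both lets that visit occur at any time on early termination. Protocol 5.6 directs discontinuing subjects through its procedures, which include vital signs, blood and urine tests.

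**Visit assignment (SAP 7.5).**
- Efficacy: Table 2 sets Week 26 at Days 162–196, target Day 183. The column is headed "Visit Window for IGA, Pruritus, % BSA(Study Day", so it covers those three variables only.
- Vital signs: "no visit window will be applied; Nominal eCRF visit will be used as analysis visit for summaries".
- Laboratory data: "When assigning the analysis visits for laboratory data, no visit window will be applied, however, the following rules will be applied". Three rules follow: samples before first application count as Screening; scheduled data come before unscheduled data; Final is derived separately. Rule 2 turns on whether scheduled data fall inside a visit window, which it does not define.

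**Outputs.**
- SAP 7.4: "Descriptive statistics for vital signs parameter will be provided for scheduled visit and for the changes from Baseline at Week 12 and Week 26".
- SAP 7.3.3: "Descriptive statistics for each laboratory parameter will be provided for scheduled visit and for the changes from Screening at each post-baseline visit". It adds mean-change plots, and "Box-and-Whisker plots for PTH and Calcium/Creatinine ratio by visit will be constructed for data exploration".
- Both sections also have a Week 26 (Final) visit, which for labs "will be defined as the last post-baseline available observation during the treatment period". The range counts use it: "The number of subjects below, within, and above the laboratory reference ranges at Screening versus Final will be summarized".

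**The concern.** The same ET visit can carry two labels. An ET visit on Day 60 is Week 8 for IGA under Table 2, but Week 26 for blood pressure and probably for PTH and calcium.

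The primary objective is safety over up to 26 weeks. Nothing inferential is planned for safety, so the descriptive tables and plots are the evidence. The laboratory data include all four key safety parameters: albumin-adjusted calcium, urine calcium:creatinine, phosphorus and PTH. A reader will take a row labelled Week 26 as the state of subjects about 26 weeks after first application. If ET values are pooled in, the row mixes early and late values.

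Vital signs and pharmacodynamic urine show this most sharply. After baseline and on treatment they are scheduled only at Week 12 and Week 26/ET. A subject who leaves before Week 12 could therefore supply a Week 26 value taken earlier than the Week 12 row. Pooling also serves little purpose, since the Final row already collects last on-treatment values.

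**Working it through.** **1. Reproduce the plan's window.** Target day = 7 × week + 1. Weeks 4, 8, 12, 20 and 26 give Days 29, 57, 85, 141 and 183, as in SAP Table 2. Midpoints of adjacent targets are (29+57)/2 = 43, (57+85)/2 = 71, (85+141)/2 = 113 and (141+183)/2 = 162. These equal the lower bounds for Weeks 8, 12, 20 and 26. The Week 26 window is thus Day 183 − 21 to Day 183 + 13. A visit held within the scheduled ±3 days falls on Days 180–186, inside it.

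**2. Trace an ET visit held before Day 162.**

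| Data | Rule in SAP 7.5 | Analysis visit |
|---|---|---|
| IGA, pruritus, %BSA | Study-day window | An earlier week (Day 60 → Week 8) |
| Vital signs | Nominal eCRF visit, no window | Week 26, unless the eCRF codes ET separately |
| Labs | No window, but rule 2 refers to one | Probably Week 26; not settled by the text |

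None of the three lab rules separates an ET sample from a Week 26 sample. If rule 2 means the ±3 days in footnote 1 of SAP Table 1, an early ET sample would not qualify. If the sentence introducing the rules governs, it would.

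**3. Size, on assumptions.** The documents give no termination rate. Let *d* be the share terminating early, spread evenly over 182 days: *d* = 25%, range 15–35%. Let *a* be the share of early leavers who attend ET, unrelated to when they leave. Everyone else attends Week 26 in window.

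- Share leaving before Day 162: *p* = *d* × 161/182.
- Share of Week 26 values taken before Day 162: *a* × *p* / (1 − *d* + *a* × *d*).

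| *d* | *p* | All attend ET (*a* = 1) | Half attend (*a* = 0.5) |
|---|---|---|---|
| 15% | 0.133 | 13% | 0.066/0.925 = 7% |
| 25% | 0.221 | 22% | 0.111/0.875 = 13% |
| 35% | 0.310 | 31% | 0.155/0.825 = 19% |

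These shares do not depend on whether enrolment is the protocol's 100 or the SAP's 140.

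**4. Direction.** If change builds with time, early values pull the row mean towards zero. If people leave because a parameter moved, their values push it the other way; Protocol 5.6 sends confirmed urolithiasis cases to this same visit. The documents do not say which would dominate.

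**The case against.** The strongest reply is that the firm text covers the less important data. Nominal assignment is stated only for vital signs, which are not among the key safety variables. For labs it is an inference, and rule 2 can be read as importing the ±3-day window. That stands: the lab half is probable, not established. It does not remove the point, because a plan that says no window applies and then uses one needs correcting, and the vital-sign rule is explicit.

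A second reply is that the protocol itself pools Week 26 with ET for labs. It does so for the shift table, under a label that says so. That does not justify a plain Week 26 row beside a separate Final row.

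A third is that full ET attendance is too generous. Protocol 5.6 asks for the assessment only where possible and lists loss to follow-up among the exit reasons. That also stands, which is why the half-attendance figures are given.

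A reader might infer three stronger things. None is supported:
- *That no row describes subjects at about 26 weeks.* Even with all attending ET, 69–87% of the row would be in window under these assumptions.
- *That the row is biased in a known direction.* It is not known.
- *That safety signals would be hidden.* Range counts use Final. Out-of-range listings, individual plots, exposure summaries and alerts to the data monitoring committee cover individual cases. What those do not give is a clean Week 26 summary.

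**Conclusion.** The point holds in a limited form. For vital signs, SAP 7.5 as written places early ET values in the Week 26 row, unless the eCRF codes ET as its own visit. For labs the same result is likely, but the text contradicts itself and must be reconciled.

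The outputs at risk are the Week 26 by-visit descriptive statistics, the lab mean-change plots, and the by-visit box plots for PTH and calcium:creatinine. The Screening-versus-Final shift table is unaffected.

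On an assumed 25% early termination, roughly one in five Week 26 values (22%) would precede Day 162 if all attend ET, and about one in eight (13%) if half do. Both figures rest on an even spread of exits. This is a labelling fault in descriptive safety output, worth correcting because the correction is cheap.

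**What to change.** In SAP 7.5:

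1. Include a lab or vital-sign value in the Week 26 row only if it was taken on Days 162–196, the existing efficacy window. The Week 26 target is common to the SAP schedule and protocol V03. Both matter, because Protocol 10.5.2 keeps already enrolled subjects on the original protocol.
2. Keep earlier ET values in Week 26 (Final), or show them in a separate ET row.
3. Reword lab rule 2 to name that window.
4. If the eCRF already codes ET as a separate visit, say so.
5. Footnote that the row describes subjects still attending at about Week 26, and should be read beside Final.

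The cost is SAP wording and minor programming, with no new data. The Week 26 row becomes smaller: about 78 per 100 at 25% termination with all attending ET (100 × (1 − 0.221)), and 87 to 69 over the 15–35% range. A visit after Day 196 drops out, as it already does for efficacy. The row also excludes early safety-driven exits, which is why the footnote and the Final row are needed. The shift table does not change.

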- The PTH returns to the normal reference range but falls below the lower limit of normal at any other stage during the course of the study

then the IDMC will be contacted for advice on management.

Subjects with abnormal serum albumin-adjusted calcium should temporarily discontinue study drug use immediately. The IDMC will be consulted for each occurrence of hypercalcemia, and depending on the severity and/or duration of the out-of-range serum calcium, will recommend appropriate management of the subject on a case-by-case basis in combination with other lab values and clinical condition of the subject in general.

Subjects with suspected kidney stones should temporarily discontinue study drug and will be referred to their Primary Care Physician (PCP) for care in tandem with Sponsor consultation of the IDMC. If urolithiasis is not confirmed, the subject may resume treatment with study drug. Subjects with confirmed urolithiasis should permanently discontinue study drug use and complete the Week 26/ET visit.

A subject who has been enrolled and assigned a kit number cannot be replaced by another subject if he/she discontinues the clinical trial for any reason.

For subjects not completing the entire study, all used (and unused) study drugs containers should be returned by the subject's parent/legal guardian to the defined personnel at the study center.

GALDERMA may also decide to prematurely terminate or suspend a subject's participation in the clinical trial.

Potential reasons for discontinuation, as listed on the Exit Form, are defined below:

- **Pregnancy:** **Withdraw the Subject from the clinical trial and follow the procedure described in Section 7.2.3.2.4**
- **Lack of Efficacy:** Investigator judgment only: based on therapeutic/disease-state expectations. If subject/parent or legal guardian opinion only, mark "subject request" and document it in the comment section of the eCRF Exit Form.
- **Adverse Event:** Complete an Adverse Event Form.
- **Subject Request:** Includes consent withdrawal, subject relocation, schedule conflicts. Explain the reason for withdrawal in the comment section of the eCRF Exit Form.
- **Protocol Violation:** Explain the violation in the comment section of the eCRF Exit Form.
- **Lost to Follow-up:** Confirmed with two documented phone calls and a certified letter (delivery receipt requested) without answer. Explain in the comment section of the eCRF Exit Form.

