### 7.2.2 Laboratory safety tests

The following laboratory safety tests will be performed according to the Schedule of Assessments (Table 2).

- Hematology:

White blood cell (WBC) count with differential, red blood cell (RBC) count, hemoglobin (Hb), hematocrit (hct), mean cell volume (MCV), and platelet count (Plt)

- Blood chemistry (non-fasting):

Total protein, alanine aminotransferase (ALT) (SGPT), aspartate aminotransferase (AST) (SGOT), alkaline phosphatase (ALP), blood urea nitrogen, creatinine (calculated creatinine clearance), and bilirubin (total and conjugated).

The Principal Investigator or another medically qualified Investigator must review and evaluate laboratory values for each subject in a timely manner. The Investigator will initial and date each laboratory report and note directly on the report whether or not each out-of-range laboratory value is clinically significant.

For each out-of-range laboratory result, the Investigator will enter in the eCRF the Investigator judgment on the presence or the absence of a clinical significance.

All out-of-range laboratory values at screening, identified as clinically significant by the Investigator, will be recorded in the medical history (report a diagnosis rather than individual laboratory parameters abnormality whenever possible).

**All out-of-range laboratory values after screening, are to be assessed for clinical significance by the Investigator (physician) or another medically qualified Investigator and to be reported as an AE if both of the following conditions are met:**

The abnormality suggests a disease and/or organ toxicity, and/or is considered pathological

AND

This abnormality was not present at the screening visit or is assessed as having worsened since the screening visit.

Unscheduled visits may occur due to laboratory result(s) that warrant further testing. If the Investigator observes a clinically relevant laboratory test value, the laboratory tests will be repeated as soon as possible and monitored until the values have returned to normal and/or an adequate explanation for the abnormality is found. This does not apply to screening laboratory test values.

An out-of-range laboratory value that is identified as clinically significant and related to the study drug(s) is considered by the Sponsor to be an Adverse Event of Special Interest (AESI) (see Section 7.2.3.1.3).

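### When a scheduled laboratory value is missing, the SAP substitutes the last unscheduled value, which is the one most likely to show recovery and may be off drug

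*SAP*

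**What the plan says.** SAP 7.5 gives three rules for assigning laboratory data to analysis visits. Rules 2 and 3 matter here.

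- **Rule 2 (by-visit rows).** "Lab data from scheduled visit will be considered first when assigning analysis visit of each scheduled visit". Only if there is none does the fallback apply: "the last of those corresponding unscheduled visit will be considered for assignment of analysis visits".
- **Rule 3 (Final).** The last scheduled on-treatment visit comes first. If its laboratory data are missing and later unscheduled data exist, "the last of those corresponding unscheduled lab data will be assigned as Final visit". If there are none: "Otherwise, the previous visit lab data will be considered in the same manner".
- **Window.** The sentence introducing the rules states: "When assigning the analysis visits for laboratory data, no visit window will be applied". Rule 2 nevertheless makes its fallback depend on a visit window.

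The protocol determines when unscheduled samples are taken and what happens to dosing meanwhile.

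- **Retesting (7.2.2).** For a clinically relevant value, "the laboratory tests will be repeated as soon as possible and monitored until the values have returned to normal and/or an adequate explanation" is found.
- **Low PTH (5.6 and 6.4).** Serum pharmacodynamic parameters are rechecked, at the investigator's and sponsor's discretion, until PTH is normal. Interrupting drug is optional.
- **Calcium (5.6).** "Subjects with abnormal serum albumin-adjusted calcium should temporarily discontinue study drug use immediately". Section 6.4 repeats this.
- **Other out-of-range results (6.4).** Interruption is optional.

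**The concern.** The fallback picks a sample by its position in a sequence whose length depends on the results. A normal make-up sample usually ends the matter, so first and last are the same value. An abnormal make-up sample starts a run of repeats that tends to stop once the value is normal, so the last differs from the first mainly when the first was abnormal. The rule then tends to replace an abnormal value with a recovered one. For albumin-adjusted calcium, that recovered value may come from a child whose drug has been interrupted.

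Safety is the primary objective. Albumin-adjusted calcium, urine calcium:creatinine ratio, phosphorus and PTH are the key laboratory parameters. The study is uncontrolled and has no inferential safety analysis, so the descriptive counts are the evidence. SAP 7.3.3 and 9.3 plan by-visit descriptive statistics, plots and one shift table (Screening versus Final), with no table of the worst post-baseline value. An abnormal value displaced by rule 2 or 3 therefore drops out of the laboratory summary tables.

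**Working it through.** The documents give no figure on this point, so there is none to reproduce. The check is a comparison of the rules, followed by an illustration of size.

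**Step 1: when the rule bites.** Four sequences at one scheduled visit:

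| Scheduled sample | Unscheduled samples | Value filed | Abnormality kept? |
|---|---|---|---|
| Abnormal | Repeats to normal | Scheduled (abnormal) | Yes |
| Missing | One, normal | That one | None to keep |
| Missing | Abnormal, then repeats to normal | Last (normal) | No |
| Missing | None | By-visit row: none; Final: step back to the previous visit | Not applicable |

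Only the third row is affected. The same abnormal result is kept if the scheduled draw succeeds and replaced if that draw is lost.

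**Step 2: is the substitute on drug?** SAP 7.3.3 defines Final as the last post-baseline observation in the treatment period. Neither that definition nor rules 2 and 3 refer to dosing at the time of sampling. For calcium, the directed interruption makes an off-drug substitute likely. For PTH, phosphorus and urine calcium:creatinine it is possible only.

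**Step 3: which unscheduled samples count?** With no laboratory window defined, nothing says which samples correspond to a missed visit. A repeat taken well afterwards, or one prompted by an abnormality at an earlier visit, could be attached to it.

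**Step 4: size.** Expected affected child-visits per parameter = V × m × h × s.

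- V = scheduled on-treatment child-visits. From protocol Table 2 and 100 children: serum at Weeks 4, 12 and 26, 100 × 3 = 300; urine calcium:creatinine at Weeks 12 and 26 only, 100 × 2 = 200.
- m = share of scheduled samples missing and made up: 5% to 10% (assumed).
- h = share of values abnormal: 6% to 10% (assumed).
- s = share of abnormal make-ups whose run ends normal: 1 gives the upper figure; 0.5 is shown for comparison (assumed).

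| | s = 1 | s = 0.5 |
|---|---|---|
| Serum, low: 300 × 0.05 × 0.06 | 0.9 | 0.45 |
| Serum, high: 300 × 0.10 × 0.10 | 3.0 | 1.5 |
| Urine, low: 200 × 0.05 × 0.06 | 0.6 | 0.3 |
| Urine, high: 200 × 0.10 × 0.10 | 2.0 | 1.0 |

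For comparison, all abnormal serum child-visits number 300 × 0.06 = 18 to 300 × 0.10 = 30. At one visit, such as Week 26, the affected number is 100 × 0.05 × 0.06 = 0.3 to 100 × 0.10 × 0.10 = 1.0 children.

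**Step 5: a harsher case for calcium.** Protocol 1.3 reports hypercalcemia in 18/74 = 24.3% of treated adults. Using that as h at one visit for 100 children, with m from 2% to 20% and s = 1, gives 100 × 0.243 × 0.02 = 0.5 to 100 × 0.243 × 0.20 = 4.9 children. The tabulated count would fall from 24.3 to between 23.8 and 19.5. This is a generous ceiling, because 24.3% is a rate per subject in adult trials, not per visit in children.

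**Step 6: means.** Protocol 1.3 puts adult calcium excesses below 10% above the upper limit of normal (ULN). Replacing one value 10% above ULN with a value at ULN moves a mean of 100 children by 10%/100 = 0.1% of ULN, and somewhat more if the recovered value lies well inside the range. The effect is on counts, not means.

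**The case against.** The strongest reply is that the route is narrow and the abnormal value is not lost. A scheduled value always has priority, so the ordinary sequence of an abnormal scheduled sample followed by repeats is tabulated correctly. Displaced values still appear in the complete listing for any subject with an out-of-range result and in the individual plots for key parameters. Hypercalcemia and PTH alerts go to the IDMC at once, and pathological values are reported as adverse events. All of this stands. It limits the size, but it does not make the last sample a sensible choice for the tables.

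The objection also rules out several stronger readings that a reader might infer.

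- *Drug is stopped whenever a laboratory value is abnormal.* Among the laboratory rules, interruption is directed only for albumin-adjusted calcium. The selection by retesting does not depend on it.
- *Tests are always repeated to normal, so the error is always favourable.* Retesting applies to clinically relevant values and may end with an explanation while the value is still abnormal. Unscheduled visits also occur for other reasons, and a normal make-up followed by a later abnormal value would be filed as abnormal. The direction is a tendency.
- *The SAP's own efficacy rule is a precedent for a better choice.* It is not. The efficacy rule takes the value closest to the target day among scheduled visits and leaves unscheduled visits out altogether.

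One further limit: dosing ends at Week 26, so a make-up draw after that visit is generally off drug whichever sample is chosen.

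**Conclusion.** The point holds in limited form and is worth correcting. Rules 2 and 3 choose the unscheduled value most likely to show recovery, with no on-drug condition, so such a value can be filed as the on-treatment or Final result. The by-visit summaries and the Screening-versus-Final shift table then tend to understate abnormality.

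Under the assumed rates, at most about 1 to 3 child-visits per serum parameter are affected, and 0.6 to 2 for urine calcium:creatinine, with fewer if some runs do not end normal. This takes all 100 children on the current protocol's visit schedule. None of the missing, abnormal or recovery rates comes from the documents. The documents do not support a claim that abnormal values are routinely removed or that they disappear from the report.

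Separately, and whatever the size of the bias, SAP 7.5 contradicts itself on whether a laboratory visit window exists, so rules 2 and 3 cannot be programmed unambiguously as they stand.

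**What to change.** In SAP 7.5, rules 2 and 3, replace the choice of the last unscheduled value with: *the first unscheduled sample on or after the scheduled (or planned) visit date, within the defined laboratory window and the treatment period*. The planned date covers a visit missed entirely.

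Define that laboratory window for each scheduled visit, and say which day closes the treatment period for this purpose. This removes the conflict between the no-window statement and rule 2, and fixes which samples correspond to a visit. If no sample qualifies for Final, keep the existing step back to the previous visit. A make-up draw after the end of treatment would then not serve as Final.

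Keep later repeats in the listings and individual plots only. No clinical rule changes.

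The cost is a reworded selection rule, a short window table and an edit to the derivation program. Protocol 9.1.2 allows SAP changes before database lock. The SAP needs revision in any case, since it still plans 140 subjects and visits at Weeks 8 and 20, against the protocol's 100 subjects and no such visits.
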